# **ADJUDICATION OF DEATHS**

All deaths require adjudication by all committee members and classification as cardiovascular vs. non-cardiovascular and sudden vs. non-sudden. If the committee finds that a death is in fact caused by stroke, this will be registered as a primary endpoint in the eCRF.

Cardiovascular death includes

- Heart failure/cardiogenic shock (pump failure)
- Sudden cardiac death witnessed
- Sudden cardiac death unwitnessed
- Other cardiovascular causes (Acute coronary syndrome, cerebrovascular accident, Peripheral Vascular Disease, Systemic embolus, Pulmonary embolus)

- Cardiac or vascular procedure complication
- Other cardiovascular death, specify
- Presumed cardiovascular death (includes events classified as "unknown" cause of death)

# Non-cardiovascular death includes

- Renal Failure
- Pulmonary (other than pneumonia)
- Pneumonia
- Sepsis
- Other infection
- Gastrointestinal (including GI hemorrhage)
- Seizure (not related to cerebrovascular accident, CVA)
- Other neurologic
- Hematologic
- Malignancy
- Non-cardiovascular procedure complication

# Definitions used to classify cardiovascular deaths

Death due to Heart Failure/Cardiogenic Shock (Pump failure):

Death occurring in the context of clinically worsening symptoms and/or signs of heart failure without evidence of another cause of death. New or worsening signs and/or symptoms of congestive heart failure (CHF) may include any of the following:

- New or increasing symptoms and/or signs of heart failure (such as dyspnea, fatigue, edema) requiring the initiation of, or an increase in, treatment directed at heart failure or occurring in a patient already receiving maximal therapy for heart failure
- Heart failure symptoms or signs requiring continuous intravenous therapy or oxygen administration
- Confinement to bed predominantly due to heart failure symptoms
- Pulmonary edema sufficient to cause tachypnea and distress not occurring in the context of an acute myocardial infarction or as the consequence of a primary arrhythmic event
- Cardiogenic shock, manifest as clinical signs and symptoms of hypoperfusion assumed to be secondary to cardiac dysfunction, and not occurring in the context of an acute myocardial infarction or as the consequence of a primary arrhythmic event
- Patients who are hospitalized and are being actively treated for heart failure and who
  have a sudden death as the terminal event will be classified as having a heart failure
  related death.

#### Sudden Presumed Cardiac Death:

Death that occurs unexpectedly in a previously stable patient will be adjudicated as witnessed or unwitnessed sudden cardiac deaths:

# Witnessed sudden cardiac death:

- Witnessed and instantaneous without new or worsening symptoms
- Witnessed within 60 minutes of the onset of new or worsening cardiac symptoms
- Witnessed and attributed to an identified arrhythmia (e.g., captured on an electrocardiographic (ECG) recording or witnessed on a monitor by either a medic or paramedic or found by interrogation of a device (ILR/ICD/CRT/pacemaker)

 Subjects unsuccessfully resuscitated from cardiac arrest or successfully resuscitated from cardiac arrest but who die without identification of a non-cardiac etiology
 Note that if a witnessed sudden cardiac death occurs as a complication of another primary cardiac process, eg, cardiogenic shock or acute myocardial infarction, the primary process will be adjudicated as the cause of death.

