# 10.7.2 Endpoint Committee:

An endpoint committee (EC) will be formed prior to study commencement to adjudicate the primary endpoints in a blinded fashion (see Appendix B and F). A neurologist and a cardiologist are appointed in the EC.

With respect to correct classification of recorded AF events an "AF adjudication committee" will be established among the cardiologists in the SC. "The AF adjudication committee" will be composed of two cardiologist (rotation among SC members will occur). If these two cardiologists disagree a third cardiologist will be involved for final adjudication of AF.

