#### Suggested device programming of parameters:

- a) FVT parameters are set at: 30/40 and a rate >222 bpm
- b) VT parameters are set at: 24 consequtive beats at a rate > 182 bpm
- c) Bradycardia is set at a rate < 30 bpm
- d) Asystolia is set at a duration > 4.5 sec
- e) Symptom activation is programmed on and programmed to 3 episodes of 7.5 min each
- f) AT/AF is programmed at AF only on
- g) Ectopy rejection is programmed off in standard settings (only programmed on in case it is observed that the device falsely categorises premature contractions as AF.

Since the LINQ Reveal has not yet been market released we do not fully know the ideal programming yet.

When the ILR reaches end of battery life the device is explanted. If a patient dies with an implanted ILR the device is explanted by a post-mortem procedure.

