# 4. Documentation for CEC adjudication

Supporting documentation required for adjudication of an event may include but is not limited to the following:

- Emergency Department records
- Pertinent laboratory reports
- Selected reports from any other test performed to evaluate the patient
- Hospital admission notes and pertinent hospital record notes surrounding the event (physician notes and nursing notes)
- Selected consultant reports and pathology reports
- Hospital or Emergency Department discharge summaries
- Death/autopsy summary
- Selected relevant hospital records
- Narrative summary of the event

The supporting documentation will have all patient identifiers (name, CPR number and information about randomization) removed or completely obscured prior to submission to the study office and supplied with a study number.

Whenever possible, suspected endpoints will be presented to the CEC only when a complete package of information has been obtained (e.g., all appropriate eCRF information and an adequate set of supporting documentation).

Adjudicators will review the documentation as hard copies.

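### The Endpoint Committee Charter admits ILR interrogation as evidence for witnessed sudden cardiac death while requiring blinded, redacted adjudication; the two rules need reconciling

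*Protocol*

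**What the plan says.** Section 10.7.2 forms the endpoint committee "to adjudicate the primary endpoints in a blinded fashion". Charter section 4 (Appendix J) applies to the documents sent for each event and requires patient identifiers ("name, CPR number and information about randomization) removed or completely obscured prior to submission to the study office").

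The charter's definition of witnessed sudden cardiac death has several alternative criteria. One of them is "Witnessed and attributed to an identified arrhythmia", with examples in brackets; the last example is an arrhythmia "found by interrogation of a device (ILR/ICD/CRT/pacemaker").

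Three other provisions matter:

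- On deaths, the charter says: "If the committee finds that a death is in fact caused by stroke, this will be registered as a primary endpoint in the eCRF".
- Appendix E says: "If a patient dies with an implanted ILR the device is explanted by a post-mortem procedure". The device has bradycardia, tachycardia and asystole detection programmed, and section 7.2.1 provides for daily remote transmissions.
- Section 3.3 expects fewer than 10% of controls to cross over to an ILR. Section 4.2 excludes anyone with a pacemaker or defibrillator at entry.

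**The concern.** The trial is open label, so blinded adjudication is the main safeguard for an endpoint that depends on judgement. The charter asks for allocation to be hidden and also names the randomised device as a source of evidence. It does not say which rule prevails, so the people preparing the packets could apply either, or vary from case to case.

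Two things are at stake. One is the blind for any death where an ILR report is shown. The other is comparability, because a rhythm recorded at death is obtainable in much of the ILR arm and in very few controls. Cause of death feeds time to cardiovascular death and the first secondary composite (section 10.2.2). A death judged to be a stroke counts in the primary endpoint.

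**Working it through.** No figure in the plan is under test here. The check compares the rules, then traces which endpoints could move, then sizes that movement under stated assumptions.

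**1. The rules side by side.**

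| If the study follows | Then |
|---|---|
| Charter section 4 (allocation obscured) | an ILR report has to be withheld, and the ILR example in the sudden-death definition cannot be used |
| The ILR example in the definition | the adjudicators see the randomised device, and the blind in section 10.7.2 is lost or badly weakened for that death |

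Both cannot be applied to the same death. Section 10.7.2 speaks of primary endpoints, but any death may become one, so the promise reaches the death packets too.

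**2. How much an ILR report reveals.** Inputs: 1,500 ILR and 4,500 control participants; 5% of the ILR group unmonitored (section 10.3); crossover at its stated ceiling of 10% (section 3.3). Assumption: anyone with an ILR is equally likely to yield a report.

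- ILR arm with a device: 1,500 × 0.95 = 1,425
- Controls with a device: 4,500 × 0.10 = 450
- Probability of ILR allocation given a device: 1,425 / (1,425 + 450) = 76%, against 25% without that knowledge

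The 76% is a floor on these inputs, since lower crossover raises it.

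**3. Which deaths are exposed.** The death must be witnessed, with a working ILR and a recorded arrhythmia, and must not already qualify otherwise. Witnessed instantaneous deaths, and deaths within 60 minutes of new or worsening cardiac symptoms, qualify with no device. The unwitnessed definition names no device data. The battery lasts three years (Appendix E), against a median follow-up of four years (section 10.3).

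**4. Which endpoints can move.** Deaths of unknown cause default to cardiovascular in both arms, and death from stroke is itself listed as cardiovascular.

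| Change caused by ILR evidence | Sudden vs non-sudden | Cardiovascular death | Stroke, embolism or cardiovascular death | Primary |
|---|---|---|---|---|
| Non-sudden cardiovascular to sudden cardiac | changes | none | none | none |
| Fatal stroke to sudden cardiac | changes | none | none | loses an ILR-arm event (favours ILR) |
| Non-cardiovascular to sudden cardiac | changes | gains an ILR-arm event (against ILR) | gains an ILR-arm event | none |

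**5. Size for the primary, no true effect.** Let *f* be the share of primary events that are fatal strokes identified through death adjudication, and *r* the fraction of these moved to arrhythmic death in the ILR arm only. Neither is in the protocol; *f* = 5–20% and *r* = 5–25% are assumed. The approximation is for a log hazard ratio with the planned 279 events at 1:3.

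- Apparent HR = 1 − *f* × *r*
- SE(log HR) = 1/√(279 × 0.25 × 0.75) = 0.138
- Probability of a false benefit = Φ(−1.96 − ln(HR)/SE), which is 2.5% without bias

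| *f* | *r* | Apparent HR | False benefit |
|---|---|---|---|
| 5% | 5% | 0.9975 | 2.6% |
| 10% | 10% | 0.99 | 3.0% |
| 20% | 25% | 0.95 | 5.6% |

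**6. Size for cardiovascular death, no true effect.** Let *q* be the ratio of non-cardiovascular to cardiovascular deaths (assumed 1 to 2) and *m* the fraction of non-cardiovascular deaths moved in the ILR arm only (assumed 2–10%). Apparent HR = 1 + *q* × *m*, from 1 + 1 × 0.02 = 1.02 to 1 + 2 × 0.10 = 1.20.

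**The case against.** The strongest reply is that this is a narrow wording conflict. ILR interrogation is one example within one of several criteria, and only for witnessed deaths. Charter section 4 already requires anything revealing allocation to be removed. If that is done, the ILR example goes unused and no harm follows. An ILR is not conclusive of arm, because some controls may receive one. Appendix E mentions explanting the device after death, but not interrogating it or forwarding the result to the committee. All of this stands, and it limits how many deaths are affected. It does not settle which rule governs, and section 4 does not name device reports among the items to obscure.

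A reader might infer more than the documents support:

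- **That the blind is broken.** It is lost only if the sudden-death definition is applied over the redaction rule, and only for those deaths.
- **That the same sudden unexplained death would be cardiovascular in one arm and something else in the other.** The charter directs unexpected deaths in previously stable patients to sudden cardiac death in both arms, and unknown causes to cardiovascular.
- **That the primary endpoint is biased towards the ILR.** No stroke definition uses device data, and the charter's definition requires a sudden focal neurologic deficit. The shift from fatal stroke to arrhythmic death is possible, but it is an inference.
- **That cardiovascular deaths in the ILR arm could be understated.** The criterion can only place a death in a cardiovascular category, so nothing in it moves a death out of that class.

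**Conclusion.** The contradiction is in the text and depends on no assumption: the ILR example in the sudden-death definition cannot be used under charter section 4 without compromising the blinding in section 10.7.2. The practical reach is limited. The main consequence is that sudden versus non-sudden death may be judged on different evidence in the two arms.

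The possible effects on the primary endpoint and on cardiovascular death run in opposite directions for the ILR. Their ranges show sensitivity to assumed inputs and are not estimates. The primary effect is small over most of its range, though at the extreme the one-sided error more than doubles. The point deserves correction because the trial is unblinded and the correction is cheap, not because a large bias has been shown.

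**What to change.** In Appendix J:

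1. Delete ILR from the device list in the witnessed sudden cardiac death definition. The other devices can stay, since either arm may receive them after entry.
2. In charter section 4, add ILR recordings and references to the ILR to the items that must be removed or obscured before documents go to the study office.
3. State that deaths are classified for the trial endpoints from evidence that can exist in both arms.
4. Report ILR terminal rhythms separately, as a descriptive analysis of the ILR arm.

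The cost is charter wording and one more redaction item when packets are prepared. The downside is that some ILR-arm deaths lose rhythm evidence in the endpoint classification, although it is kept for the descriptive report. The change is best made before deaths are adjudicated, because reviewers who have seen an ILR report cannot be re-blinded to it.

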# Unwitnessed Sudden Presumed Cardiac Death:

An unwitnessed death is one that occurs in a patient who, when last seen alive, within an observation period of 72 hours:

• Did not manifest another life-threatening non-cardiac disease (e.g., infectious, metabolic disorders);

#### and/or

- Did not reveal a cause other than cardiovascular (e.g., trauma) at the scene of death; and/or
  - Death was ruled cardiovascular in cause on an autopsy report or death certificate, and occurred in the absence of pre-existing circulatory failure or other modes of death.

If an unwitnessed sudden cardiac death occurs, information regarding the patient's clinical status within the week preceding death should be reviewed for potential insight into the primary cause of death.

# Non-Sudden Death due to Other Cardiovascular Causes:

These are defined from medical records and include acute coronary syndrome, cerebrovascular accident (stroke), peripheral vascular disease, systemic embolus, pulmonary embolus, cardiac or vascular procedure complication, other specified cardiovascular death

#### Non-Sudden Presumed Cardiovascular Death:

All deaths not attributed to the categories of cardiovascular death and not attributed to a noncardiovascular cause, are presumed cardiovascular deaths and as such are part of the cardiovascular mortality endpoint.

# Definitions used to classify non-cardiovascular deaths

Non-cardiovascular death is defined as any death not covered by cardiac death or vascular death and includes the following:

- Renal Failure
- Pulmonary (other than pneumonia)
- Pneumonia
- Sepsis
- Other infection
- Gastrointestinal (including GI hemorrhage)
- Seizure (not related to CVA)
- Other neurologic
- Hematologic
- Malignancy
- Non-cardiovascular procedure complication
- Other (specify)

Non CV death will primarily be reported as yes or no. In cases where patients are admitted to hospital for a cardiovascular reason and dies with an infection the event will be classified as CV death.
